4.3 Missing Data

Every effort will be made to keep missing data, particularly the Day 90 outcome assessments, to a minimum. However, some missing data may be inevitable due to, for example, loss to follow-up.

All imputed values will be determined prior to database lock and conducting primary analyses via the rules documented prospectively in this Statistical Analysis Plan for the study.

To incorporate death as part of the estimand definition following the composite strategy, deceased participant will be assigned a score 6 on the mRS, 42 on the NIHSS and 0 on Barthel Index and be counted as non-responders. In addition, deceased participants are considered as experiencing worsening of stroke. Thus, there will be no missing mRS, NIHSS, BI or worsening of stroke data due to death.

No imputation is planned for safety data. Efficacy outcomes will be imputed using a datainformed imputation as follows:

4.3.1 Imputation of Mortality and Worsening of Stroke

For the analysis of rate of mortality, for participants for whom the mortality status is not known at Day 90:

- if they were alive at Day 30, then the subject will be imputed as alive at Day 90
- if both the Day 30 and Day 90 mortality is status is missing, the participant will be imputed as Dead at Day 90.

Worsening of stroke data will be imputed similarly:

- if it's unknown whether the subject experienced worsening of stroke by Day 90 while they did not report any worsening of stroke by Day 30, then the subject will be imputed as not experiencing worsening of stroke at Day 90.
- if both worsening of stroke status is unknown at both Day 30 and 90, then the subject will be imputed as experiencing worsening of stroke at Day 90.

No imputation will be done on the missing one-year follow-up mortality data.

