7.2 Participant Discontinuation/Withdrawal from the Trial

Participation in this clinical trial may be discontinued for any of the following reasons:

- Administrative reasons (uncooperative, noncompliant, etc.)
- Participant's decision not to participate any further
- If it is in the participant's best interest, per the qualified/principal or sub-investigator

If the participant or legally authorized representative (LAR) withdraws consent, participant data will be included in the analysis up to the date of the consent withdrawal and this withdrawal of consent will be documented in the CRF.

If the LAR has originally provided consent and the participant subsequently declines consent, this will be deemed to be a withdrawal of consent. The investigator and sponsor would continue to have access to data that have already been collected.

A participant may not withdraw use of his or her data that have already been collected, this is in alignment with the FDA guidance document "Data Retention When Participants Withdraw from FDA-Regulated Clinical Trials", which is based on the importance of avoiding selection biases that could compromise the analysis of the overall trial.

Otherwise, all randomized participants will continue to be followed according to protocol requirements and follow-up data will be included in the analysis. Criteria for removal of participants will be recorded and reported.

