9.3.1 General Considerations

All imputed values will be determined prior to database lock and conducting primary analyses via rules documented prospectively in the final Statistical Analysis Plan for the study.

Deceased participant will score 6 on the mRS, 42 on the NIHSS and 0 on Barthel Index and be counted as non-responders. Every effort will be made to keep missing data, particularly the Day 90 outcome assessments, to a minimum.

For the primary analysis, for participants who are missing the mRS at Day 90:

- if the participant is known to be dead at Day 90, they will be considered to be a non-responder and the mRS will be imputed as 6
- if the mRS was obtained at the Day 30 assessment or later, it will be carried forward as the Day 90 mRS value
- if both the Day 30 and Day 90 mRS scores are missing but the participant is documented to be alive at Day 90 they will be considered to be a non-responder and the mRS will be imputed as a 5
- if both the Day 30 and Day 90 mRS scores are missing and the mortality status of the participant is unknown at Day 90 they will be considered to be a non-responder and the mRS will be imputed as a 6.

If more than 5% subjects randomized are missing the mRS score at Day 90, additional imputation methods will be employed- details of which will be included in the SAP.

For the secondary analysis of rate of mortality, for participants for whom the morality status is not known at Day 90:

- if they were alive at Day 30, then the subject will be imputed as alive at Day 90
- If both the Day 30 and Day 90 mortality is status is missing, the participant will be imputed as Dead at Day 90.

For other analyses involving the mRS (other than mortality), the same imputation approach will be taken as for the primary analysis. No imputation will be done on the missing one-year follow-up mortality data.

A number of events may occur after study drug initiation and during the 90-day trial observation period that could impact data completeness, the interpretation of, or the ability to observe, each outcome variable. Details of handling of such events, which may or may not meet the ICH definition of intercurrent events (IEs)⁴², will be provided in the SAP.

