3.2 Mortality

Mortality status will be obtained at all visits during the 90-day study period and at the One-Year follow up. Specifically, it will be assessed at Day 6 or discharge and at Days 30 and 90. Mortality rate is defined as the number of deaths observed divided by the number of subjects observed over the 90-day study period between nerinetide and placebo control subjects.

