6.2.1 Mortality

Mortality rates, defined as the number of deaths observed divided by the number of participants observed over the 90-day study period between nerinetide and placebo control participants. Results will be summarized and tabulated.

In addition to the primary and sensitivity analysis, mortality analysis will be additionally supported using:

- Time-to-death survival function analysis, both unadjusted using Kaplan-Meier analysis and adjusted via Cox proportional hazards regression. Subjects who are known to be alive or the mortality status is unknown at study completion/discontinuation will be censored at the date of completion/discontinuation.
- Unadjusted logistic regression as described for the primary estimand

Mortality status scores will be listed by treatment arm and subject.

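### The main Day 90 mortality analysis counts as dead anyone with neither Day 30 nor Day 90 vital status, even if last documented alive at discharge or at withdrawal

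*Combined protocol and SAP*

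**What the plan says.** Two rules in SAP 4.3.1 apply when Day 90 vital status is unknown. The first is "if they were alive at Day 30, then the subject will be imputed as alive at Day 90". The second is "if both the Day 30 and Day 90 mortality is status is missing, the participant will be imputed as Dead at Day 90". Protocol 9.3.1 has the same second rule: "If both the Day 30 and Day 90 mortality is status is missing, the participant will be imputed as Dead at Day 90". SAP Table 4 makes the analysis with this imputation the primary analysis of Day 90 mortality, in the ITT population. Table 1 and SAP 6.2 place mortality first among the secondary endpoints in the fixed sequence. SAP Table 5 uses the same imputation at the interim.

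Other parts of the plan bear on who is caught by the rule:

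- On when mortality is recorded, SAP 3.2 says "Specifically, it will be assessed at Day 6 or discharge and at Days 30 and 90". Status before Day 30 is therefore collected.
- On regained-capacity consent, protocol 7.2 says "If the LAR has originally provided consent and the participant subsequently declines consent, this will be deemed to be a withdrawal of consent". The schedule of activities seeks that consent from the Day 2/3 visit onward.
- On data after withdrawal, protocol 7.2 says "participant data will be included in the analysis up to the date of the consent withdrawal".
- Protocol 7.3 asks sites to seek the vital status of every randomized participant where law and ethics allow, and permits public sources.

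Other analyses treat the same people differently. For the time-to-death analyses, SAP 6.2.1 says "Subjects who are known to be alive or the mortality status is unknown at study completion/discontinuation will be censored at the date of completion/discontinuation". SAP 4.3 says "No imputation is planned for safety data", and 90-day mortality is also a main safety outcome (protocol 9.3.3, SAP 7).

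**The concern.** A participant enrolled on a representative's consent may regain capacity, decline to continue before Day 30, and leave no later trace. That person was alive and able to decide when last seen, yet the main mortality analysis records a death. The same holds for someone discharged alive and then lost. The Day 6/discharge status that the trial collects plays no part in the rule.

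Two things are at stake. Death is a hard endpoint, and here part of the event count would come from missing forms rather than from deaths. Mortality also opens the secondary sequence, so if it fails, the three secondary endpoints after it become exploratory.

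**Working it through.** **The passages side by side.** Take one ITT participant, documented alive at Day 6/discharge, who withdraws on Day 10 and whose vital status is not found later.

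- Main mortality analysis (SAP 4.3.1, Table 4): dead.
- Definition of the rate (SAP 3.2 and 6.2.1, protocol Table 9-1): observed deaths over participants observed. This person is not an observed death.
- Kaplan-Meier and Cox (SAP 6.2.1): censored alive at discontinuation.
- Safety mortality (SAP 4.3 and 7): no imputation, so not a death.
- SAP 4.3.2 regards missing-at-random as reasonable for missing mRS that is not due to death. SAP 4.3.1 takes the opposite view for vital status.

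**The plan's own power figure.** The documents state no power for mortality. The 91.3% for the primary endpoint (protocol 9.1) reproduces with Z bounds 2.668 and 1.981 at 60% information. For 50% versus 61.4%, power is 91.3% with 833 participants (850 less 2%) and 91.9% with 850. For 50% versus 61.14% with 850, it is 90.6%.

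**Inputs for mortality.**

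- 850 participants, 425 per arm (protocol 9.1).
- Dropout/non-evaluable rate 2%, which is 0.02 × 850 = 17 people (protocol 9.1).
- Prior-trial reduction among participants not given alteplase: 7.5 points absolute, 39.7% relative (protocol 2.1.5). Placebo mortality is then 7.5/0.397 = 18.9%, and nerinetide mortality 18.9 − 7.5 = 11.4%.
- Assumption: a fraction m of each arm lacks both statuses. I take m = 2% and show 1% and 5%.

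**Equal missingness.** Counted mortality is p′ = (1 − m)p + m.

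- At m = 2%, placebo is 0.98 × 0.1889 + 0.02 = 20.5% and nerinetide is 0.98 × 0.1139 + 0.02 = 13.2%. The difference is 0.98 × 7.5 = 7.35 points.
- The imputed share of counted deaths is 2 × 0.02/(0.2051 + 0.1316) = 11.9%.
- Power (unadjusted, two-sided 0.05) is Φ[(Δ − 1.96·SE₀)/SE₁], with SE₀ pooled and SE₁ unpooled. Under the rule, (0.0735 − 1.96 × 0.02567)/0.02554 = 0.91, giving 81.8%. With observed cases (416.5 per arm), (0.075 − 1.96 × 0.02484)/0.02470 = 1.07, giving 85.7%. With complete follow-up, power is 86.3%.
- Range, rule versus observed cases: 84.1% versus 86.0% at m = 1%; 74.9% versus 84.6% at m = 5%.

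**Unequal missingness, 17 people, same assumed effect.** The pooled Z is 3.05 with nobody missing. By placebo/nerinetide split of the missing:

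| Split | Z |
|---|---|
| 17/0 | 4.19 |
| 12/5 | 3.41 |
| 9/8 | 2.94 |
| 5/12 | 2.32 |
| 0/17 | 1.54 |

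**No true effect.** With 15.1% mortality in both arms and a 12/5 split, counted rates are (0.1514 × 413 + 12)/425 = 17.5% and (0.1514 × 420 + 5)/425 = 16.1%, a spurious 1.4 points. One-sided error rises from 0.025 to about 0.08.

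**A smaller number, 8 people.** From 80 versus 48 deaths (Z = 3.07), a 6/2 split gives 3.37, 4/4 gives 2.99, 2/6 gives 2.62 and 0/8 gives 2.25.

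**The case against.** The rule's reach is limited. To be counted dead, a participant must have no Day 30 status, no Day 90 status, and not be found by the search in protocol 7.3. Anyone known alive at Day 30 is counted alive. The number could be close to zero.

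The rule is also pre-specified, blind to arm, and in line with the mRS rule that assigns 6 when scores and vital status are all missing. SAP Table 4 already plans adjusted observed-cases, per-protocol, Kaplan-Meier and Cox analyses for mortality, each labelled as sensitivity or supportive. Efficacy and safety counts could differ anyway, because the safety population is grouped by treatment received.

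Most of this stands and limits the size of the problem. It does not remove it. None of the alternative analyses carries the alpha, the rule overrides information the trial holds, and the result does not fit the plan's own definition of the endpoint.

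A reader might go further in four ways that the documents do not support:

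- *Everyone who declines consent is counted dead.* Only those without status at both dates are.
- *The imputed deaths gather in the nerinetide arm because more of those participants recover capacity.* No data bear on this. Withdrawals by representatives might be commoner among sicker participants, so either direction is possible.
- *The rule would overturn the mortality result.* With 8 people affected, even the 0/8 split leaves Z = 2.25, above 1.981. Among the splits shown, only 0/17 loses significance.
- *The same people are certainly scored as worsening of stroke.* SAP 4.3.1 scores no event if none was reported by Day 30, and an event if status is unknown at both dates. It does not say which applies after an event-free hospital stay.

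**Conclusion.** The concern holds in a limited form. The alpha-protected mortality analysis assigns death to people whose last documented status may be alive, against the plan's own definition and its handling of the same people elsewhere. At the assumed 2% missing in both arms, about 12% of counted deaths would be imputed and power would fall by about 4 points against observed cases (81.8% versus 85.7%). Unequal missingness could weaken a real effect or inflate an apparent one, so the rule is not reliably conservative. These sizes rest on the prior-trial mortality rates, an unadjusted test, and the assumption that every planning dropout lacks both statuses. The documents give no rate of missing vital status or of declined consent.

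**What to change.** In SAP 4.3.1 and protocol 9.3.1, before any interim unblinding:

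- Do not set unknown status to dead in the main mortality analysis. Keep the covariate-adjusted model. Either multiply impute unknown Day 90 status from treatment, baseline covariates and last known vital status (Day 6/discharge or withdrawal date), or make the already planned adjusted observed-cases analysis the main one. A Kaplan-Meier risk difference would also avoid imputed deaths, but if unadjusted it would drop the planned covariate adjustment.
- Keep the unknown-counts-as-dead rule as a sensitivity analysis.
- In SAP 6.2.1, censor at the date last known alive.
- For worsening of stroke, state that a documented event-free hospital stay counts as known status, so that the rule for status unknown at both dates does not override it.
- Report documented deaths by arm beside the efficacy estimate, so that efficacy and safety mortality can be reconciled.
- Apply the same handling in SAP Table 5 for the interim.

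No new data collection is needed, and SAP 4.3.2 already sets out multiple imputation for mRS response that can be adapted. The cost is SAP wording, a re-ordering of analyses, and a matching protocol edit, which needs ethics approval under protocol 10.1.1. The main estimate would then assume missingness at random for a few participants. The retained worst-case analysis covers that.

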7.3 Lost to Follow up

A participant will be considered lost to follow-up if he or she repeatedly fails to return for scheduled visits/contacts and is unable to be contacted by the study site. The following actions must be taken if a participant fails to return to the clinic or if they cannot be contacted by phone for a required study visit:

- The site must attempt to contact the participant and reschedule the missed visit/contact as soon as possible and counsel the participant on the importance of maintaining the assigned visit schedule and ascertain whether or not the participant wishes to and/or should continue in the trial.
- Before a participant is deemed lost to follow up, the investigator or designee must make every effort to regain contact with the participant (at a minimum 3 telephone calls/contacts). These contact attempts should be documented in the participant's study record.

- Should the participant continue to be unreachable, he/she will be considered to have withdrawn from the trial.
- Site personnel will attempt to collect the vital status of the participant within legal and ethical boundaries for all participants randomized, including those who did not get study intervention. Public sources may be searched for vital status information. If vital status is determined as deceased, this will be documented and the participant will not be considered lost to follow-up. Sponsor personnel will not be involved in any attempts to collect vital status information.

8 STUDY ASSESSMENTS and PROCEDURES

Study procedures and their timing are summarized in the Schedule of Activities. Adherence to the trial design requirements is essential and required for study conduct.

Procedures conducted as part of the participant's routine clinical management (e.g., blood count) and obtained before signing of the ICF may be utilized for baseline purposes provided the procedures met the protocol-specified criteria and were performed within the time frame defined in the Schedule of Activities.

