The shift parameters that result in a reversed study conclusion (i.e. from statistically significant to non-significant) will be flagged. Alternate series of shift parameters may be applied based on the actual data.

The missing mRS data at one-year follow-up will be handled according to below:

- If subjects are known to be dead before or at one-year follow-up visit, mRS will be assigned a score of 6 and counted as non-responders.
- Other missing data not due to death will be imputed by the multiple imputation method as described above.

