6.6.2 Mortality Rate at 1 Year

Mortality at 1 year will be assessed as per the protocol (from family or legally authorized representative or from hospital records). It will be analyzed and reported as described in Section 6.2.1.

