	Day 90 EQ-VAS	ANCOVA, ITT, OC	N/A	N/A
1 Year	mRS Responder (≤2 vs. >2)	Adjusted log-binomial regression model, ITT, MI	N/A	N/A
	Day-90 Mortality	Adjusted log-binomial regression model, ITT, OC	N/A	N/A
	Barthel Index	Adjusted log-binomial regression model, ITT	N/A	N/A
	EQ-VAS	ANCOVA, ITT, OC	N/A	N/A

*For analyses using the adjusted log-binomial regression model, a Poisson model with robust variance will be used if the log-binomial model fails to converge

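### The 1-year mortality analysis in SAP Table 4 drops participants of unknown status, so it is likely to overstate mortality in each arm, and it conflicts with SAP 6.6.2

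*Combined protocol and SAP*

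**What the plan says.** **Missing 1-year mortality.** SAP 4.3.1 says "No imputation will be done on the missing one-year follow-up mortality data", and protocol 9.3.1 gives the same rule.

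**Model.** The 1 Year block of SAP Table 4 lists mortality as "Adjusted log-binomial regression model, ITT, OC", with N/A in both the sensitivity and supportive columns. The row is labelled as Day-90 mortality, although it sits among the 1-year endpoints.

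**Cross-reference.** SAP 6.6.2 says of 1-year mortality: "It will be analyzed and reported as described in Section 6.2.1". Section 6.2.1 defines the rate as deaths over participants observed and adds Kaplan-Meier and Cox as further support. There, participants alive or of unknown status "will be censored at the date of completion/discontinuation".

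**Day 90 rule.** SAP 4.3.1 has two branches for unknown status: "if they were alive at Day 30, then the subject will be imputed as alive at Day 90"; and if both visits are missing, "the participant will be imputed as Dead at Day 90". An observed-case analysis is the Day 90 sensitivity analysis in Table 4.

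**1-year mRS.** Known deaths score 6. For the rest, SAP 4.3.2 says: "Other missing data not due to death will be imputed by the multiple imputation method as described above".

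**Tracing.** Protocol 7.3 has sites try to establish vital status for everyone randomized: "Public sources may be searched for vital status information". A participant found to have died is not counted as lost; one who stays unreachable is treated as withdrawn.

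**The concern.** Death is permanent, so a death recorded at any earlier visit leaves no unknown status at Day 365. The unknowns at 1 year are therefore mostly people last seen alive. Under an observed-case rule they leave the denominator, the deaths stay in the numerator, and the proportion drifts upward. The rule also discards what is known about those people, namely survival to Day 90 or later.

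One lost participant can meet three rules: imputed alive or dead at Day 90, excluded from 1-year mortality, and multiply imputed for 1-year mRS. The two 1-year results then rest on different participants, although SAP 6.6 presents the sub-study as support for the Day 90 outcomes. A reader of the second report could take the 1-year mortality percentages at face value, with no companion analysis listed in Table 4.

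**Working it through.** The plan gives no figure for 1-year mortality or 1-year loss, so there is none to reproduce on this point. The check is how far an observed-case proportion departs from the true one.

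**Inputs**
- Day 90 mortality *d*: protocol 2.1.5 reports for the prior trial's no-alteplase group an absolute reduction of 7.5% and a relative one of 39.7%. Placebo = 0.075/0.397 = 18.9%; nerinetide = 18.9 − 7.5 = 11.4%.
- Assumed, not in the documents: mortality *h* = 5% from Day 90 to 1 year in reached survivors; a fraction *u* = 2% to 20% of Day 90 survivors unreached; mortality *q* in the unreached.
- The only dropout figure is 2% (protocol 9.1), and it concerns the primary endpoint.

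**Formulas**
- True = d + (1−d)[(1−u)h + uq]
- Observed-case (OC) = [d + (1−d)(1−u)h] / [1 − (1−d)u]
- Hence OC − True = (1−d)u × (OC − q)

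**Equal loss, q = h = 5%.** True rates: nerinetide 0.114 + 0.886×0.05 = 15.8%; placebo 0.189 + 0.811×0.05 = 22.9%; RR 0.690. Worked case, nerinetide at u = 10%: (0.1139 + 0.8861×0.9×0.05)/(1 − 0.0886) = 0.1538/0.9114 = 16.9%.

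| Unreached | OC nerinetide | OC placebo | Excess, points | OC RR |
|---|---|---|---|---|
| 2% | 16.0% | 23.2% | 0.2 / 0.3 | 0.689 |
| 5% | 16.3% | 23.7% | 0.5 / 0.8 | 0.689 |
| 10% | 16.9% | 24.5% | 1.1 / 1.6 | 0.688 |
| 20% | 18.2% | 26.4% | 2.3 / 3.5 | 0.687 |

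(Excesses are from unrounded rates.) The relative risk, which is what the log-binomial model reports, hardly moves. The risk difference goes from −7.1 to −7.7 points at 10% and −8.3 at 20%.

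**Unequal loss, q = h = 5%.** With 5% of nerinetide and 15% of placebo survivors unreached, OC rates are 16.3% and 25.4%, RR 0.642. With the losses swapped they are 17.5% and 23.7%, RR 0.737. The true RR is 0.690 in both.

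**When the sign reverses.** By the identity above, OC overstates only while q is below the OC rate: 16.9% nerinetide and 24.5% placebo at u = 10%. At q = 25%, true nerinetide = 0.1538 + 0.0886×0.25 = 17.6% against OC 16.9% (understated), and true placebo is 24.6% against 24.5%.

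**Kaplan-Meier by comparison.** If the unreached were last documented alive at Day 90, Kaplan-Meier gives d + (1−d)h, that is 15.8% and 22.9%, whatever q is. Its error is (1−d)u × (h − q). It is nearer the truth than OC while q lies closer to h than to the OC rate. At u = 10% that means q below (5 + 16.9)/2 = 10.9% for nerinetide and (5 + 24.5)/2 = 14.8% for placebo.

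**Against the Day 90 rule.** With 5% missing and a 15% observed-case rate, that rule gives 0.95×15 = 14.25% if all the missing were alive at Day 30, and 14.25 + 5 = 19.25% if all lacked both visits. It can fall on either side of observed cases.

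**The case against.** The strongest reply is that observed cases are not the only 1-year analysis. SAP 6.6.2 imports 6.2.1, where lost participants contribute time until they are censored. That is correct, and a reader who infers from Table 4 that nothing else is planned goes further than the SAP allows. But 6.2.1 makes Kaplan-Meier and Cox additional to a proportion of participants observed, and Table 4 lists no supportive analysis at 1 year. The two places disagree, and the observed-case model remains the main one.

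A reader might also infer that mortality must be overstated. The documents do not show that. Tracing through family, hospital records and public sources can document survival as well as death, and the unreached may include unrecorded deaths. Upward bias remains the likelier case: to reverse it, people who had already survived to Day 90 would need later mortality above a rate that counts every death since randomization.

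Nor is the 1-year rule the opposite of the Day 90 rule. That rule has two branches, with observed cases as its sensitivity analysis, and declining to carry survival from Day 90 to Day 365 is defensible. The rules differ, and that is all.

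Finally, nothing in the documents suggests that loss will differ by arm, since 1-year assessors stay blinded or firewalled (protocol 6.3.1, SAP 1.7). At 2% loss the excess is only 0.2 to 0.3 points. SAP 6.6 also requires a table of deaths, losses and withdrawals between the two populations. These points limit the consequence but do not remove the conflict between Table 4 and 6.6.2.

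**Conclusion.** The point holds in limited form. As summarised in Table 4, the 1-year mortality analysis excludes unknown status with no companion analysis and is likely to overstate arm-level mortality. The excess is about 0.2 to 3.5 points across 2% to 20% unreached, assuming Day 90 mortality as in the prior trial, 5% later mortality, and similar mortality in reached and unreached survivors.

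The documents do not support reading this as a bias in favour of nerinetide. With equal loss the relative risk stays within 0.687 to 0.689 against 0.690; with unequal loss it moves in either direction. Nor can one say that every known death is retained: the 1-year population is limited to participants with valid sub-study consent, which could remove some deaths.

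The 1-year analysis is supportive and outside the fixed testing sequence (SAP 4.1, 6.2, 6.6), so no primary or secondary Day 90 claim depends on it. The change is still worth making because the better analysis is already named in the SAP.

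**What to change.** In SAP Table 4 and 6.6.2:

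- Make Kaplan-Meier 1-year estimates by arm, with their difference and confidence interval, and the Cox model the main 1-year mortality analysis.
- Censor participants of unknown status at the date last documented alive. The 6.2.1 wording refers to study completion or discontinuation. At 1 year that could be read as Day 90 completion, or as the later date on which someone was declared lost. Also state the day at which the estimate is read, since the contact window is Day 365 ± 30 days.
- Keep the observed-case log-binomial model as a sensitivity analysis. The two methods err differently if the unreached have high mortality, so showing both is informative.
- Relabel the row as 1-year mortality.

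The multiple imputation planned for 1-year mRS should not be borrowed. It imputes responder status, not vital status, so a new model would be needed.

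The cost is SAP wording. Both methods are already specified, and the no-imputation rule in SAP 4.3.1 and protocol 9.3.1 can stand, because censoring is not imputation. The one operational check is that the case report form captures a last-known-alive date.
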